### 15.1.2. Part B Study Design and Procedures

Following Visit 16 (Week 52), subjects who elect to continue in Part B, the long-term extension, will return to the site at 12-week intervals until pegcetacoplan is commercially available for the disease under study. Specific assessments for Part B are listed in Table 7.

The vaccination history for each subject should be reviewed prior to entry into the long-term extension, as described in Section 9.1.4, and any additional required vaccinations should be administered according to the current ACIP guidelines.

Subjects who discontinue treatment early should complete an early termination visit immediately following discontinuation (but no later than 6 weeks after discontinuation of treatment) and 1 exit visit 6 weeks after the early termination visit, as outlined in Table 7.

#### 15.1.3. Part B Dose Rationale

The long-term extension maintains the same dose for Part A, which is described in Section 8.2.

## 15.1.4. Part B Study Treatments

This section contains study treatment information for Part B, the long-term extension.

### 15.1.4.1. Part B Identity of Investigational Product

The test product is pegcetacoplan, which will be provided as a sterile solution of pegcetacoplan (54 mg/mL) in acetate-buffered sorbitol, supplied in stoppered glass vials. Additional information regarding the investigational product is provided in the pegcetacoplan IB.

### 15.1.4.2. Part B Pegcetacoplan Dosing

Dosing will remain the same as Part A: subjects will continue to receive SC infusions pegcetacoplan at a dosage of 1080 mg twice weekly.

Dosing diaries will be utilized for pegcetacoplan and are to be completed for each dose administered at the study site or outside of regular clinic visits. Subjects should ideally maintain a consistent dosing schedule and should not delay or defer dosing. Missed doses will be handled on a case-by-case basis between the investigator and medical monitor, with the general approach being to administer a missed dose as soon as noticed, unless the next dose has already been administered.

## 15.1.4.3. Part B Pegcetacoplan Administration

Pegcetacoplan will be administered as a 20-mL SC infusion. The preferred site of infusion will be the abdomen; however, if a subject does not tolerate administration to the abdomen, alternative sites may be considered.

Subjects may choose to continue to self-administer pegcetacoplan infusions at the study site on scheduled dosing days when a study visit coincides, although this is not required. Self-administration conducted at the study site will be supervised to ensure that the subject continues to remain compliant with the administration guidelines.

### 15.1.5. Part B Labeling, Packaging, Storage, and Handling

#### 15.1.5.1. Part B Labeling

Labels containing study information and pack identification are applied to the investigational product(s) container.

All investigational product is labeled with a minimum of the following: protocol number, dosage form (including product name and quantity in pack), route of administration, directions for use, storage conditions, batch number, packaging reference, the statements, "For clinical trial use only," and/or "CAUTION: New Drug—Limited by Federal (or US) Law to Investigational Use," and name and address of the sponsor.

Space is allocated on the label so that the site representative can record a unique subject identifier and date dispensed by the site to the subject.

Additional labels may, on a case-by-case basis, be applied to the investigational product in order to satisfy national, local, or institutional requirements, but they must not:

- Contradict the clinical study label
- · Obscure the clinical study label
- · Identify the study subject by name

Additional labels may not be added without the sponsor's prior full agreement.

#### 15.1.5.2. Part B Packaging

Investigational product is supplied in 20-mL glass vials. Please refer to the pharmacy manual for details.

Changes to sponsor-supplied packaging prior to dosing may not occur without full agreement, in advance, by the sponsor.

### 15.1.5.3. Part B Infusion Supplies

The sponsor will supply syringes, vial adapters, infusion sets, and ambulatory syringe infusion pumps, as required. Refer to the pharmacy manual for further details.

### 15.1.5.4. Part B Storage and Handling

The investigational product should be stored refrigerated at 2-8 °C, both at home and in the clinic. Temperature monitoring is required at the investigator site (or documented storage location) to ensure that the investigational product is maintained within an established temperature range.

The investigator or appropriately qualified site staff will be responsible for the following:

- ensuring that the investigational product is stored in a secure, limited-access location at the site
  - limited responsibility may be delegated to the pharmacy or member of the study team, but this delegation must be documented
- ensuring that the temperature is monitored throughout the duration of the study and that records are maintained

A pharmacist or appropriately qualified designated person will be responsible for the following:

- storing the investigational product appropriately
- dispensing the vials of investigational product to the subject
- entering the unique subject identifier on the investigational product bottle/carton labels as they are distributed

When the subject receives the investigational product from the site, it should be transported in a sponsor-approved bag or box, containing previously temperature-conditioned cold plates to ensure that the storage temperature (2-8 °C) is maintained. Temperature monitoring will not be required during transport or at the subject's residence, but a log will be kept for every infusion to ensure that all investigational product was kept refrigerated.

ULN	Upper Limit of Normal
uPCR	Urine Protein-to-Creatinine Ratio
WHO	World Health Organization

1. INTRODUCTION

This statistical analysis plan (SAP) provides a technical and detailed elaboration of the statistical analyses of efficacy, safety, and pharmacokinetic/pharmacodynamic data as described in the study protocol Amendment 3 dated 03 February 2022. Specifications for tables, figures, and listings are contained in a separate document.

There are two parts of this study: Part A includes an approximate 8-week screening period to be followed by a 52-week main period, during which time Group 1 will have pegcetacoplan administration for all 52 weeks and Group 2 will receive pegcetacoplan administration only following the Week 12 biopsy through the remainder of the main period. All subjects then enter the 8-week follow-up period or the long-term extension (Part B).

The total duration of participation is up to 68 weeks (not including the Part B long-term extension).

For analysis purposes, data will be summarized by treatment groups and overall. When applicable (and it will be specified in the following sections), the summary tables will be further separated by the 3 treatment phases (Part A Controlled Portion, Part A Noncontrolled portion, and Part B long-term extension) and combined.

2. OBJECTIVES AND ENDPOINTS

2.1. Objectives

2.1.1. Primary Objective

The primary objective of this study is to evaluate the efficacy of pegcetacoplan in improving the underlying pathophysiology of C3G/IC-MPGN after 12 weeks of treatment.

2.1.2. Secondary Objectives

The secondary objectives of the study are as follows:

- to evaluate the effect of pegcetacoplan on key clinical manifestations of the disease after 52 weeks of treatment
- to evaluate the safety of pegcetacoplan for up to 52 weeks in subjects with recurrent C3G/IC-MPGN in a renal allograft

2.1.3. Exploratory Objectives

The exploratory objectives are to characterize the additional clinical, laboratory, and histologic findings of C3G/IC-MPGN in response to pegcetacoplan, including pegcetacoplan pharmacokinetic, pharmacodynamic, and immunogenicity in patients with C3G/IC-MPGN.

2.2. Endpoints

2.2.1. Primary Endpoint

The primary efficacy endpoint is the proportion of subjects with reduction in C3c staining on renal biopsy after 12 weeks of treatment with pegcetacoplan.

2.2.2. Secondary Endpoints

The secondary endpoints are as follows:

Safety:

- Safety measured by AEs, clinical laboratory tests, vital signs, and ECGs

Efficacy:

- The proportion of subjects with reduction in C3c staining on renal biopsy after 52 weeks of treatment
- Changes from baseline biopsy in C3c staining over time
- The proportion of subjects with stabilization or improvement in estimated glomerular filtration rate (eGFR) over time
- The proportion of subjects with stabilization or improvement of serum creatinine concentration over time
- Changes and percentage changes from baseline in eGFR and serum creatinine concentration over time

2.2.3. Exploratory Endpoints

The exploratory endpoints are as follows:

- For subjects with baseline proteinuria above the upper limit of normal (ULN), the proportion of subjects achieving at least a 50% reduction in proteinuria over time
- For subjects with baseline proteinuria above the ULN, the proportion of subjects achieving complete clinical remission of proteinuria after 12 and 52 weeks of treatment, defined as normalization of proteinuria
- Changes and percentage changes in proteinuria over time
- Change over time in additional key biopsy features, including:
 - Glomerular myeloid cell infiltration
 - Glomerular macrophage infiltration (as measured by CD68 staining)
 - Glomerular crescents (in subjects with crescents)
 - Mesangial expansion and hypercellularity
 - Deposits by electron microscopy
 - Activity score (based on C3G histologic index)
 - Chronicity score (based on C3G histologic index)
- Ophthalmology:
 - Change in maximum drusen size at Week 52
 - Number of intermediate or large drusen at baseline and Week 52
- The number and incidence of rejection episodes in each group
- The number and incidence of graft loss in each group
- Pegcetacoplan serum concentrations over time
- Change in complement biomarkers (50% classical hemolytic complement pathway activity [CH50] and 50% alternative hemolytic complement pathway activity [AH50]) over time
- Immunogenicity: The incidence of anti-pegcetacoplan antibodies and incidence of anti-PEG antibodies (including treatment-emergent and treatment-boosted responses) throughout the treatment and follow-up periods

3. STUDY DESIGN

This Phase 2, multicenter, open-label, randomized, controlled clinical study is designed to evaluate the safety and efficacy of pegcetacoplan in subjects who have post-transplant recurrence of C3G or IC-MPGN. There will be up to 12 subjects enrolled in this study. This study has two parts.

Part A (Core Study):

- Screening Period: an up to 8-week screening period, during which a screening renal allograft biopsy will occur
- Main Period: a 52-week study period that contains 2 portions (Controlled and Non-Controlled) during which subjects will be randomized to either Group 1 or Group 2 at the Week 1 visit:
 - Controlled Portion: Weeks 1-12 of the study
 - Group 1: Up to 9 subjects will be randomized to this treatment group and will receive pegcetacoplan treatment throughout the entire study; biopsies will occur at Week 12
 - Group 2: Up to 3 subjects will be randomized to this treatment group and will not receive pegcetacoplan treatment during the Controlled Portion; biopsies will occur at Week 12
 - Non-Controlled Portion: Weeks 13-52 of the study
 - Group 1: Subjects will continue to receive pegcetacoplan treatment; biopsies will occur at Week 52
 - Group 2: Subjects will receive pegcetacoplan treatment following their Week 12 renal allograft biopsy; biopsies will occur at Week 52
- Follow-up Period: an 8-week follow-up period.

Part B:

Any subject who, in the opinion of the investigator is experiencing clinical benefit from pegcetacoplan administration may participate in Part B, a long-term extension, in order to continue to receive treatment with pegcetacoplan until it is commercially available for the disease under study. If invited to participate, the subject can enter Part B as soon as his/her 52-week treatment period has ended and does not need to participate in the 8-week follow-up period.

3.1. General Description

This is an open-label, randomized, controlled, Phase 2 study, consisting of a single cohort of up to 12 subjects with clinical and pathologic evidence of recurrent C3G or IC-MPGN in a renal allograft. Subjects will be randomized 3:1 to Group 1 (pegcetacoplan treatment throughout the Main Period) or Group 2 (no pegcetacoplan treatment for the first 12 weeks of the Main Period, followed by pegcetacoplan treatment), respectively. The visit schedule will be the same, regardless of randomization.

Pathologic evidence of recurrence requires a biopsy-based diagnosis of C3G or IC-MPGN in the renal allograft, confirmed by a central pathologist. The diagnosis need not be the same in the native kidney and the renal allograft; for example, a subject with C3G in the native kidney and IC-MPGN post-transplant is still eligible for the study.

Subjects with either preexisting disease recurrence or upon initial identification of clinical and pathologic recurrence of disease will be invited to enter screening. Subjects must also have an eGFR of at least 15 mL/min/1.73m² and no more than 50% fibrosis on renal biopsy.

The study will require a total of 3 renal allograft biopsies, during screening, Week 12, and Week 52. Flexibility has been built-in for each biopsy as described below:

[figure not shown]
- Screening renal allograft biopsy: must occur within 4 weeks leading up to the day of randomization
 - A non-study biopsy may be used as the baseline biopsy provided it meets the following criteria:
 - it was performed no more than 12 weeks prior to Week 1
 - the subject has remained clinically stable since the biopsy with no changes in medication regimens that would be expected to significantly alter the baseline biopsy findings
 - the prior biopsy is available for central pathology review and includes all the required components of a study baseline biopsy.
- Week 12 renal allograft biopsy: must occur at a time point between Weeks 12 and 14, inclusive; Group 2 subjects cannot begin pegcetacoplan administration until after the biopsy occurs
- Week 52 renal allograft biopsy: must occur at a time point between Weeks 48 and 52, inclusive, but after completion of the 24-hour urine collection scheduled for Week 48.

In the event that a subject has a biopsy for clinical cause within the timeframe allowed for a study biopsy, this clinical biopsy may be able to serve as one of the protocol biopsies, provided it includes all required components for this study. If it is not able to serve as a protocol biopsy, then information from that biopsy should still be collected within the study database, if possible.

After completion of the 52-week Main Period, any subject who, in the opinion of the investigator, is experiencing clinical benefit from pegcetacoplan administration will be invited to participate in Part B, the Long-Term Extension Phase in order to continue to receive treatment with pegcetacoplan until it is commercially available for the disease under study (see Protocol Section 15). Those who do not continue on pegcetacoplan in the long-term extension protocol will enter a Follow-Up period of a minimum of 8 weeks.

Figure 1: Study Design

Screening (up to 8 weeks)	Main Period		Follow-Up (8 weeks)
	Controlled (12 weeks)	Non-Controlled (40 weeks)	

Abbreviation: R = randomization.

3.2. Randomization

Subjects will be randomized 3:1 to Group 1 (pegcetacoplan treatment throughout the Main Period) or Group 2 (no pegcetacoplan treatment for the first 12 weeks of the Main Period, followed by pegcetacoplan treatment), respectively.

3.3. Blinding

This is an open-label study (not blinded).

3.4. Sample Size

Given the exploratory nature of the study, no formal statistical hypothesis testing will be performed; therefore, the sample size is not based upon statistical power of the study. Up to 12 subjects will be enrolled into this study.

3.5. Analysis Timing

The analysis of data from the Part A Controlled Portion of the study will be performed when all subjects have completed the Part A Controlled Portion or discontinued early and all corresponding data have been entered into the database, reviewed, cleaned, and finalized, and the Week 12 Analysis database locked. At that time, the primary analysis will be performed, which will include all efficacy and safety analyses for the Part A Controlled Portion. For Week 12 Analysis, all summary tables will be presented by randomized group.

The analysis of data from the Part A Non-Controlled Portion will be performed once all subjects have completed the Part A Non-Controlled Portion or discontinued early and all corresponding data have been entered into the database, reviewed, cleaned, and finalized, and the Week 52 Analysis database locked. For disposition, baseline summary, and efficacy analysis, tables will be presented similarly as Week 12 Analysis.

The table summaries for protocol deviations, concomitant medications, study drug exposure and compliance, as well as all AE summaries will be presented in 5 columns: (1) Group 1's Part A Controlled Portion results; (2) Group 1's Part A Non-Controlled Portion results; (3) Group 2's Part A Non-Controlled Portion results; (4) Part A Non-Controlled Portion results combined (in other words, combining columns 2 and 3); (5) for all results since Pegcetacoplan injection (in other words, combining columns 1 and 4). More details on the summary layout are provided in the separate table shell document.

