5.5. Exposure to Investigational Product

The following parameters will be summarized using the Safety Set and listed:

- Total dose administered (mg)
- Duration of treatment with pegcetacoplan (days) defined as (last infusion date – first infusion date + 1)
- Number and percentage of subjects who received at least one infusion
- Number and percentage of subjects with any infusions missed
- Number and percentage of subjects with one or more incomplete infusions
- Number and percentage of subjects with any infusions interrupted

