7. SAFETY ANALYSIS

7.1. Adverse Events

Treatment-emergent adverse events (TEAEs) are defined as those AEs that develop or worsen after the first dose of study medication (or after randomization in Group 2) and up to 56 days beyond the last dose of study medication. Analysis of AEs (as discussed below) will be limited to TEAEs, but data listings will include all AEs regardless of their timing.

All reported AEs will be coded using the current version of MedDRA and summarized by System Organ Class (SOC) and Preferred Term (PT). All summaries by SOC and PT will be ordered by decreasing frequency of subjects within each SOC and then similarly by decreasing frequency of subjects within each PT. In the case of equal frequency of number of subjects in SOC or PTs, summaries of TEAEs will be sorted alphabetically. Rules for handling missing severity, relationship to study drug, relationship to infusion procedure, outcome, and missing dates of AEs are described in Section 13.

If a PT was reported more than once for the same subject, that subject would only be counted once in the incidence for that PT. For subjects experiencing the same PT at multiple severities, the occurrence of the AEs with the greatest severity will be used in the analysis of incidence by severity. For subjects experiencing the same PT at multiple relationship levels, the occurrence of the AEs with the strongest relationship to study drug will be used in the analysis of incidence by relationship to study drug.

The AE summaries will be presented by treatment group and overall. The number and incidence of rejection episodes and graft loss will also be summarized.

An overall summary for TEAEs including number of subjects who experience a TEAE, number of total TEAEs and number of unique TEAEs will be provided:

- TEAE
- Treatment-related TEAE
 - Related
 - Not related
- Infusion-related TEAEs
 - Related
 - Not related
- Serious TEAE
- Maximum severity of TEAEs
- Infusion site reaction (yes/no)
- TEAE leading to treatment discontinuation
- TEAE leading to dose interruption
- TEAE leading to study discontinuation
- TEAE leading to death

The following summaries will be provided:

- TEAEs by SOC and PT
- TEAEs by PT in decreasing order of frequency
- Treatment-related TEAEs by SOC and PT
- Infusion-related TEAEs by SOC and PT
- Serious TEAEs by SOC and PT
- TEAE by SOC, PT and maximum severity
- TEAE leading to treatment discontinuation by SOC and PT

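### The Week 52 adverse event tables set a 12-week column beside 40-week and pooled columns with no person-time, so later columns can look worse at unchanged risk

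*SAP*

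**What the plan says.** SAP 3.5 describes two analyses. At Week 12 all tables are shown by randomised group. For the Week 52 analysis, all AE summaries, along with exposure, compliance and some other tables, "will be presented in 5 columns":

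1. Group 1, Controlled Portion
2. Group 1, Non-Controlled Portion
3. Group 2, Non-Controlled Portion
4. columns 2 and 3 together
5. "for all results since Pegcetacoplan injection (in other words, combining columns 1 and 4")

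The period lengths are in SAP 3 ("Controlled Portion: Weeks 1-12 of the study") and in the design figure in SAP 3.1 ("Non-Controlled (40 weeks")). Group 2's start on drug depends on its biopsy, which "must occur at a time point between Weeks 12 and 14, inclusive; Group 2 subjects cannot begin pegcetacoplan administration until after the biopsy occurs" (SAP 3.1).

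On the metric, SAP 7.1 says that if a preferred term (PT) recurs in a subject, "that subject would only be counted once in the incidence for that PT". The overall TEAE summary adds numbers of events. SAP 13.1 makes the percentage denominator the subjects in the analysis set. SAP 5.5 summarises "Duration of treatment with pegcetacoplan (days) defined as" last minus first infusion date plus one, but SAP 7.1 makes no use of it. Neither the SAP nor Protocol 12.4 plans an exposure-adjusted rate or an equal-length window.

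**The concern.** A crude percentage of subjects with an event grows with the time they are watched. Columns 1 and 2 hold the same Group 1 subjects, first for 12 weeks and then for 40. Placed side by side, they invite the question whether risk rises with continued treatment. Crude figures will tend to suggest that it does even when nothing has changed, and they can hide a real fall. Column 5 adds a further mixture: up to 52 weeks on drug for Group 1 and about 38 to 40 weeks for Group 2.

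Safety to Week 52 is a secondary objective (SAP 2.1.2), and Protocol 12.1 says that the data are meant to support further clinical studies. A misreading of these tables could therefore carry forward.

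**Working it through.** **Period lengths (the plan's own figures).** Weeks 1 to 12 are 12 weeks. Weeks 13 to 52 are 52 − 13 + 1 = 40 weeks. 12 + 40 = 52, which agrees with SAP 3 and 3.1. The ratio is 40/12 = 3.33.

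**Assumption.** The documents give no AE rate. I assume a constant hazard that is the same in both periods, no dropout, and a range of 12-week risks p12.

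**Crude percentages.** Under that assumption p40 = 1 − (1 − p12)^(40/12). For p12 = 20%: 1 − 0.80^3.33 = 52.5%, and 52.5/20 = 2.62.

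| 12-week risk | 40-week risk | Ratio |
|---|---|---|
| 1% | 3.3% | 3.29 |
| 10% | 29.6% | 2.96 |
| 20% | 52.5% | 2.62 |
| 30% | 69.5% | 2.32 |
| 40% | 81.8% | 2.04 |
| 50% | 90.1% | 1.80 |
| 80% | 99.5% | 1.24 |
| 90% | about 100% | 1.11 |

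Setting the ratio to 3 and to 2 gives p12 = 8.9% and 41.7%. For true 12-week risks of 1/9, 2/9 and 3/9, the ratios are 2.92, 2.55 and 2.22. The limit for rare events is 3.33.

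**Event counts.** At a constant event rate, the expected count in the same nine subjects rises by 40/12 = 3.33 from column 1 to column 2.

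**Other lengths of the later period.**
- 38 weeks (late Group 2 start): the ratio is between 2 and 3 for p12 of about 5% to 40%.
- 48 weeks (40 plus 8 weeks, if follow-up events within the 56-day TEAE window of SAP 7.1 are placed in the Non-Controlled column): the band is about 19% to 46%, and the rare-event limit is 48/12 = 4.0.

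**A fall that crude figures hide.** Suppose that 20% of subjects have an event in 12 weeks and 40% in 40 weeks. The percentage has doubled. The implied rates, at 52.18 weeks per year, are −ln(0.80)/12 × 52.18 = 0.97 and −ln(0.60)/40 × 52.18 = 0.67 per patient-year, a fall of about 31%.

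**Person-time by column (9 and 3 subjects, no dropout).**

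| Column | Subject-weeks | Patient-years |
|---|---|---|
| 1 | 9 × 12 = 108 | 2.07 |
| 2 | 9 × 40 = 360 | 6.90 |
| 3 | 3 × 40 = 120 | 2.30 |
| 4 | 12 × 40 = 480 | 9.20 |
| 5 | 9 × 52 + 3 × 40 = 588 | 11.27 |

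With these denominators the ratio under a constant hazard is 1.0 by construction. Precision is poor. One event in column 1 is 1/2.07, or about 48 per 100 patient-years, with an exact Poisson 95% interval of roughly 1 to 269.

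**The case against.** The strongest reply is that little is hidden or at stake.

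- Event counts are planned as well as percentages, and exposure is tabulated in the same five columns, so a reader can see the imbalance and form a rough rate.
- Every AE is listed by subject, for at most 12 subjects.
- The randomised safety comparison is in the Week 12 Analysis, over equal periods.
- Columns 2, 3 and 4 are all about 40 weeks long.
- No test is planned on any of these contrasts.
- Rates from about 2 patient-years may mislead more than percentages do.
- The table shells are a separate document and could already contain person-time.

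Much of this stands. It confines the point to the Week 52 tables, mainly column 1 against the later columns and the pooled column 5. A reader might infer that the plan shows nothing but subject numbers and percentages, or that the comparison with untreated controls is distorted. The documents support neither.

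What remains is that the counts have no time denominator, so within Group 1 they carry the full 3.3-fold difference. Tabulated treatment duration is not time at risk, because TEAEs are collected for 56 days after the last dose. The SAP commits to no rate in the shells. Imprecision affects the planned percentages too, and showing person-time makes it plain.

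**Conclusion.** The point holds as a limited presentational defect in the Week 52 AE tables. At unchanged risk, the 40-week percentage exceeds the 12-week one by a factor of about 1.0 to 3.3, and event counts in the same subjects rise by about 3.3. This rests on a constant hazard, no dropout and a 40-week later period.

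A reader might infer that later columns will in general look two to three times worse. The documents do not support that, because they give no AE rate. The factor is 2 to 3 only for 12-week risks of about 9% to 42%, such as a PT with a true risk of 1 to 3 in 9. For a row such as any TEAE, which most subjects may have, the inflation is small. For rare events it is larger than threefold.

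The change is worth making because safety to Week 52 is a stated objective and the remedy is cheap and descriptive. It does not bear on the primary endpoint or on the randomised comparison.

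**What to change.** In SAP 7.1, add to the Week 52 TEAE overview table, for each of the five columns:

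- person-time at risk, in patient-years;
- events per 100 patient-years for overall, serious, treatment-related and infusion-related TEAEs.

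Define person-time to match the TEAE window: from the start of the period to the earliest of the end of the period, study exit, or 56 days after the last dose. Do not use the infusion-based duration of SAP 5.5. State when Group 2's clock starts in columns 3 to 5, since its first dose can fall as late as about Week 14. State also whether follow-up events count in the Non-Controlled columns, so that numerator and denominator agree.

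Rates of first events are optional, because they need person-time censored at the first event for each category and column. No rate is needed for Group 2's control period, which is not among the five columns.

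The cost is a small new derivation from dosing, visit and AE dates, with no change to trial conduct. The rates will be very imprecise, so they should be printed with their person-time and read descriptively.
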